3.1. Dates and Points of Reference

3.1.1. Definition of Baseline

The randomization visit for the study takes place after the 2-weeks run-in period. Unless stated otherwise, baseline data are defined as the last data collected prior to the time and/or on the date of first randomized dose, which is usually the same day as the Day 1 Predose/Baseline Visit for scheduled measurements. If baseline data at Day 1 predose/Baseline visit are missing, the last non-missing data prior to dosing (including data from Screening) will be used as baseline.

The data collected in the single-blind placebo run-in period will not be analyzed unless they are considered baseline data for randomized patients. For NPRS and DSIS, the baseline data are defined as the weekly mean prior to the first randomized dose.

3.1.2. Study Day

Study Day 1 is defined as the date of receiving the first randomized dose.

- Study Day
 - For a date on or after Study Day 1
 Study Day = (Date of Interest) (Study Day 1) + 1
 - For a date before Study Day 1Study Day = (Date of Interest) (Study Day 1)

The quantity 'days since the first randomized dose' is defined as:

days since first dose = visit (or event) date - Study Day 1 + 1

The quantity 'days since the last randomized dose' is defined as:

• days since last dose = visit (or event) date - date of last dose

For summaries that present distribution of time expressed in weeks and months, weeks are defined as days divided by 7 and months are defined as days divided by 30.4375.

3.1.3. Analysis Visit Windows

Data from early termination visits and unscheduled visits will be assigned to an appropriate scheduled postbaseline visit using a windowing scheme for assessments that are tabulated or summarized by visit. Scheduled visits will not be windowed.

Numeric pain rating scale (NPRS) and daily sleep interference scale (DSIS) are collected daily using an e-diary form. The daily scores will be mapped to an analysis "Week" according to the following windows defined by Study Day in conjunction with study phases described above. Subjects are instructed to report the NPRS number that best indicates the average intensity of neuropathic pain over the last 24 hours throughout the study daily at bedtime. Subjects also complete the DSIS via their e-diary daily upon waking.

The weekly mean is defined as the sum of non-missing daily scores divided by the number of days with non-missing scores for that week. Subjects with fewer than 3 daily scores during an analysis week will be considered to have a missing weekly mean for that week.

The analysis window for efficacy endpoints will be defined based on the schematic as follows:

Table 2: Analysis Visit Window for weekly NPRS average pain intensity

Visit	Lower Bound in Study Day (inclusive)	Upper Bound in Study Day (inclusive)
Run-in period	First record during run-in period	-1
Randomized/treatm	ent period	
Baseline	-7	-1
Week 1	1	7
Week 2	8	14
Week 3	15	21
Week 4	22	28
Week 5	29	35
Week 6	36	42
Week 7	43	49
Week 8	50	56

Week 9	57	63				
Week 10	64	70				
Week 11	71	77				
Week 12 (EOT)	78	84				
Follow-up period						
Week 13	85	91				
Week 14	92	98				
Week 15	99	105				
Week 16 (EOS)	106	112				
Week 16 (EOS)	106	112				

Note1: the NPRS number that best indicates the average intensity of neuropathic pain over the last 24 hours throughout the study daily at bedtime, recorded using e-dairy.

Note 2: Run-in visit is intended to describe run-in phase average pain score prior to first dosing in randomized phase.

Note 3: All available data will be used to calculate the weekly average mean up to Week 12 regardless of treatment discontinuation per ITT principle.

Note 4: If the last study dose for a patient is beyond the defined windowing for Week 12, only off study treatment days will be used to calculate off study treatment follow-up weekly mean.

Table 3: Analysis Visit Window for DSIS

Visit	Lower Bound in Study Day (inclusive)	Upper Bound in Study Day (inclusive)			
Run-in period	First record during run-in period	-6			
Randomized/Treatment period					
Baseline	-6	1			
Week 1	2	8			

Week 2	9	15			
Week 3	16	22			
Week 4	23	29			
Week 5	30	36			
Week 6	37	43			
Week 7	44	50			
Week 8	51	57			
Week 9	58	64			
Week 10	65	71			
Week 11	72	78			
Week 12 (EOT)	79	85			
Follow-up period					
Week 13	86	92			
Week 14	93	99			
Week 15	100	106			
Week 16 (EOS)	107	113			

Note 1: Subjects complete the DSIS in the e-diary daily upon waking prior to daily dose.

Note 2: Run-in visit is intended to describe run-in phase average DSIS score prior to first dosing in randomized phase

Note 3: All available data will be used to calculate the weekly average mean up to Week 12 regardless of treatment discontinuation per ITT principle.

Note 4: If the last study dose for a patient is beyond the defined windowing for Week 12, only off study treatment days will be used to calculate off study treatment follow-up weekly mean.

Table 4: Analysis Visit Window for Safety,

Visit	Lower Bound Study Day (inclusive)	Upper Bound Study Day (inclusive)	Target Day
Baseline ^(a)	Last record prior to dosing	Last record prior to dosing	1
Week 1*	2	12	8
Week 2	13	21	15
Week 4	22	35	29
Week 6	36	49	43
Week 8	50	63	57
Week 10	64	77	71
Week 12 (EOT)	78	91	85
Week 16 (EOS)	92	135	113

Note 1: Assessments are collected at scheduled in-clinic visit (target day) per protocol

Note 2:

Note 3: Following Day 1, ECG is only collected at Week 1, Week 12 (EOT) and Week 16 (EOS)

For unscheduled visits, if more than one observation is within the same window, the observation closest to the target day will be used.

However, if both the observations are equally distant from the target day, the latest one will be used if applicable or the average of both observations will be used; if repeated measurements are on the same day, then the last measurement will be used.

Mapping visits may be handled case by case as well, if appropriate.

If ≥ 2 assessments are available at a scheduled visit, then the mean of the assessments will be used for the analysis.

Early termination visits and unscheduled visits for safety data will be mapped in a similar way as above.

Descriptive statistics by visit for vital signs, ECG, lab data will be summarized based on scheduled visits once unscheduled and early withdrawal visits are determined, as described above.

Unless being mapped to missing scheduled visits or specified, the assessments at unscheduled visits will not be used in the summary statistics but will be listed.

3.2. Study Treatment

Study drug, dosage, and mode of administration:

- RTA 901 capsules 10 mg orally once daily
- RTA 901 capsules 80 mg orally once daily
- Matching Placebo orally once daily

Each dose of study drug should be administered at approximately the same time each day and will be recorded in the e-diary. All doses should be taken in an early fasted state, defined as having no food within at least 2 hours prior to study drug administration and 1 hour following study drug administration.

3.3. Study Periods

3.3.1. Screening Period (Days -28 to -15)

The Screening Period Includes 1 clinic visit up to 2 weeks prior to the Run-in Period (within 28 $[\pm 2]$ days prior to Day 1). Daily NPRS and DSIS will be collected using an e-diary from Screening to the end-of-study visit. Washout from prohibited medications is allowed if the Investigator deems it medically appropriate; the washout period must cover 5 half-lives of the prohibited medication and must be completed prior to the last 7 days of Screening.

3.3.2. Run-in Period (Days -14 to -1)

The Run-in Period includes 1 clinic visit which must occur during a 14 (\pm 2)-day period prior to Day 1. Subjects who continue to successfully meet the Run-in eligibility criteria will receive single-blind placebo once daily in the morning in addition to their SOC pain medication. All study drug should be administered in an early fasted state, defined as having no food within at

least 2 hours prior to study drug administration and for 1 hour following study drug administration. Daily NPRS scores will continue to be collected using the e-diary. Pain intensity and rescue medication use will also continue to be recorded daily at bedtime in the e-diary. Subjects will also complete the DSIS upon waking. Subjects in Part 1 who remain eligible after the Run-in period will be randomized 1:1:1 to either RTA 901 (10 or 80 mg) or placebo at Day 1 (randomization).

3.3.3. Treatment Period (Day 1 to Week 12/EOT)

The Treatment Period includes 8 clinic visits over 12 weeks. Within Part 1, subjects who successfully meet the randomization eligibility criteria will be randomized using randomization and trial supply management and stratified by SOC pain medication on Day 1. Post randomization, study drug will be dispensed according to the Schedule of Assessments.

Week 12/Day 85 will be the end of treatment (EOT) visit.

3.3.4. Follow-up/End of Study (Week 16/EOS)

The Follow-up Period includes 1 clinic visit on Day 113 ± 2 , which must occur approximately 4 weeks following the EOT visit.

3.4. Key Derived Variables

3.4.1. Laboratory Evaluations Imputations

Any laboratory assessments less than the lower limit of detection (i.e., < LLD) are imputed as LLD/2. If no LLD is available, then the imputed value is the minimum numeric value listed divided by 2 (e.g., < 25 is 25/2=12.5). Laboratory assessments above the ULD are imputed as the ULD. If the lab result is qualitative but presented as > X and X is 10 times greater than the ULN or the ULN is not present, then the value X is used in the analysis.

3.4.2. Electrocardiogram Fridericia Corrected QT Interval

Electrocardiogram intervals are assessed locally at each site. The following formula is used to calculate the QTcF interval for analysis from QT and RR intervals:

•
$$QTcF = QT/\sqrt[3]{RR}$$

where RR = 60 / (Heart Rate).

3.5. Stratification Factors and Subgroup Variables

3.5.1. Stratification Factors

The populations are stratified according to a standard of care (SOC) pain medication: duloxetine or pregabalin/gabapentin. Subjects entering the study must be taking duloxetine, pregabalin, or gabapentin.

3.5.2. Subgroup Variables

Subgroup analyses for NPRS average maybe performed to evaluate the consistency of the findings if appropriate on the ITT population. The baseline subgroup factors may include but not limited to:

- Age categories (<65 years, >=65 years)
- Sex (female, male)
- Ethnicity (Non-Hispanic/Latino; Hispanic/Latino)
- Race (White, Non-White)
- Standard of Care (duloxetine, pregabalin/gabapentin)
- Diabetes type (type 1, type 2)
- Baseline NPRS category (<7,>=7)
- Baseline DSIS category (<7, >=7)
- Duration of DPNP (by median)
- Baseline MNSI (by median)

If one of the subgroups has fewer than 10 subjects, then the corresponding subgroup analyses will not be performed.

3.6. Analysis Sets

Intent-to-Treat Analysis Set (ITT)

The ITT analysis set is defined as all randomized subjects who receive at least 1 dose of randomized study drug. The ITT analysis population will be used for the primary, secondary and exploratory efficacy endpoints. In analyses performed on the ITT analysis set, participants will be analyzed according to their planned treatment group.

Per-protocol set

The per-protocol population will include the ITT subjects who do not have any major protocol deviations deemed to meaningfully impact efficacy assessments. Subjects will be analyzed by randomized treatment.

Major protocol deviations that could impact efficacy include the following, although further efficacy-related deviations may be identified prior to treatment unblinding at database lock:

 Failing/meeting at least one relevant inclusion/exclusion criterion that could impact efficacy

• <80% or >120% treatment compliance during DB period based on time on treatment

• Prohibited medication use that could impact efficacy

Using of rescue medication over the prespecified daily limits during Run-in and treatment period:

- Acetaminophen/paracetamol not to exceed 3000 mg per day;
- Ibuprofen not to exceed 1200 mg per day (protocol version 3.0);
- Ibuprofen not to exceed 600 mg per day (protocol version 4.0).

A per-protocol analysis of the primary endpoint will be performed.

Safety Analysis Set

The safety analysis set includes all randomized subjects who receive at least 1 dose of randomized study drug. The safety analysis set will be used for evaluation of safety variables. In analyses performed on the safety analysis set, participants will be analyzed according to their actual treatment received. Subjects who receive at least 1 dose of RTA 901 will be classified in the RTA 901 group.

4. List of Planned Study Analyses

4.1. Primary Analysis

After completion of Part 1 end of study visit (Week 16) for all randomized subjects, the formal planned analyses will be conducted to evaluate the safety, tolerability, efficacy, of RTA 901 (10 mg or 80 mg) versus placebo.

5. Statistical Methods for Planned Analyses

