### 8. STATISTICS

### 8.1. Sample Size Estimate

This study will be conducted in 2 parts. A total of approximately 192 subjects (64 subjects per treatment arm) are planned for randomization in Part 1 and approximately 192 subjects (64 subjects per treatment arm) are planned for randomization in Part 2, for a total of 384 subjects to be randomized. This sample size is based on a dose-ranging scheme to evaluate initial safety, efficacy, of RTA 901 in this population. The primary comparisons for efficacy are between each of the 2 RTA 901 treatment groups and the placebo treatment group. The overall Type I error rate will be controlled at the 0.05 significance level. A hierarchical testing strategy to control the overall Type I error will be defined in the SAP. Power calculations are based on a 2-sample t-test with no adjustments for multiple comparisons. The study assumes a difference in NPRS pain intensity means of 1.2 between each RTA 901 treatment group and the placebo treatment group and a standard deviation of 2.4.

If doses selected for Part 2 do not include doses studied in Part 1, then an analysis by dose group for Part 1 or Part 2 doses will be performed following completion of each study part. Within each Part, with 64 subjects per treatment group, each study part has 80% power to compare treatment groups to placebo.

If doses selected for Part 2 include any doses studied in Part 1 (ie, 10 or 80 mg), then an analysis by dose group will be performed using Part 1 and Part 2 combined, following completion of the study. The dose group that is enrolled in both parts will have 128 subjects. With 128 placebo subjects compared to 128 subjects in the RTA 901 dose group, there is 98% power to detect the same difference (1.2 NPRS points) assuming the same standard deviation (2.4). RTA 901 dose groups that are enrolled in only 1 part will have 64 subjects. With 128 placebo subjects compared to 64 subjects in each RTA 901 dose group, there is 90% power to detect the same difference (1.2 NPRS points) assuming the same standard deviation (2.4).

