# 8.3. Endpoints and Objectives

The SAP will describe in detail the methods used for the primary, safety, secondary, and exploratory endpoints and will serve as the final arbiter of all statistical analyses. The study endpoints are listed in Section 2.2.

Data will be summarized using descriptive statistics. Continuous data will be summarized with statistics such as mean, standard deviation, median, minimum, and maximum. Categorical data will be summarized using frequency counts and percentages.

If doses selected for Part 2 include any doses studied in Part 1 (ie, 10 or 80 mg), then the final analysis by dose group will be performed following final study database lock. Otherwise, if doses selected for Part 2 do not include doses studied in Part 1 then final analysis by dose group for Part 1 or Part 2 doses will be performed following the Part 1 or Part 2 database lock, respectively.

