5.1. General Principles

Descriptive summary statistics will be presented for all primary, secondary, and exploratory endpoints collected by visits and treatment group per schedule of assessment. Unless otherwise specified, for continuous endpoints, the summary statistics will generally include number of participants with data, mean, standard deviation, median, first and third quantiles and range. For categorical endpoints, the summary statistics will generally include number of participants with data, frequency counts and the percentage of those with data in each category. Analyses will be performed on the data from Part 1 alone.

The statistical software, SAS® Version 9.4 or above, will be used for all summaries and statistical analyses.

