6.2. Multiplicity Control

A sequential stepwise testing will be performed on the primary endpoint for RTA 901 group (80mg, 10mg) compared to placebo in the following testing order to control the overall type I error at two-sided alpha level of 0.05:

- Step 1: Comparison of 80 mg group versus placebo group. If p-value <0.05, then proceed to Step 2. If not, testing for subsequent step is considered as exploratory.
- Step 2: Comparison of 10 mg group versus placebo group.

No formal testing will be performed for the secondary endpoints.

6.3. Primary endpoint of change from baseline in NPRS average pain intensity at week 12

The primary endpoint is the change from baseline in the average daily NPRS pain intensity score during Week 12.

The NPRS of pain intensity is a numeric scale, ranging from 0 (representing no pain at all) to 10 (representing the worst pain imaginable). The subject selects a whole number (0 to 10) that best indicates the intensity of their neuropathic pain in the past 24 hours. Subjects will report how they perceive their average neuropathic pain intensity during the past 24 hours at bedtime.

The weekly mean is defined as the sum of non-missing daily scores divided by the number of days with non-missing scores for that week. Subjects with fewer than 3 daily scores during an analysis week will be considered to have a missing weekly average for that week.

No imputation will be conducted at weekly mean level.

The MMRM model will include baseline NPRS score, visit, treatment, the interaction of treatment and visit, the interaction of baseline NPRS score and visit. The analysis visit will include all visits (study week) up to week 12 during double-blinded treatment period. An unstructured covariance (UN) matrix will be used to model the within-subject variability. Model convergence will be checked. If the unstructured covariance model fails to converge with the Newton-Raphson algorithm after increasing the default maximum iterations, the Fisher scoring algorithm will be used to provide initial values of the covariance parameters.

If the model does not converge with an unstructured covariance matrix, then the analysis visit will include weeks 1, 2, 4, 6, 8, 10 and 12 per protocol scheduled assessment visits.

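### The SAP formally tests Part 1 at the full 0.05 but does not say how that test relates to the protocol's pooled analysis if 10 or 80 mg recurs in Part 2

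*SAP*

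**What the plan says.** **SAP.** Section 4.1 sets the timing: "After completion of Part 1 end of study visit (Week 16) for all randomized subjects, the formal planned analyses will be conducted". Section 5.1 sets the data: "Analyses will be performed on the data from Part 1 alone". Section 6.2 tests 80 mg against placebo and then, if p is below 0.05, 10 mg against placebo, in order "to control the overall type I error at two-sided alpha level of 0.05". None of these sections depends on which doses go into Part 2. Section 2.4 says that Part 1 serves to inform dose selection. Section 1 leaves Part 2 to a separate SAP and allows its design to change after the Part 1 results. Section 9 lists one change from the protocol, the definition of the intent-to-treat set.

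**Protocol.** Sections 8.1 and 8.3 have two branches.
- If neither 10 nor 80 mg recurs, each part is analysed after its own lock.
- If either recurs, "then an analysis by dose group will be performed using Part 1 and Part 2 combined, following completion of the study". Section 8.3 adds the timing: "then the final analysis by dose group will be performed following final study database lock". Doses used in one part only are included: "RTA 901 dose groups that are enrolled in only 1 part will have 64 subjects", and these are compared with 128 placebo subjects from both parts.

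Section 8.4.2 promises control of the overall type I error at 0.05 and leaves the hierarchy to the SAP. Section 8.3 says that the SAP "will serve as the final arbiter of all statistical analyses".

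**The concern.** On the recurrence branch, following both documents means that the same dose is tested formally on Part 1 and then again on pooled data that contain the same Part 1 subjects. The SAP spends the whole 0.05 on the first test. No text divides alpha between the two, makes one supersede the other, or says whether a Part 1 p-value is final, interim or only descriptive. SAP 2.4 points to dose selection; SAP 4.1 and 6.2 point to a formal result.

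At stake is the overall 0.05 that both documents promise, and the reader's ability to tell which p-value is the trial's result for a dose. Recurrence is a realistic case. Part 2 doses come from a range of 1 to 80 mg, which contains both Part 1 doses, and the protocol gives separate power figures for it.

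**Working it through.** **1. Inputs.** Difference 1.2, SD 2.4, 64 per arm per part, 1:1:1 (protocol 8.1 and 4.5); two-sided 0.05 with 80 mg first (SAP 6.2).

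**2. The protocol's powers.** Noncentral t, with noncentrality 1.2 / [2.4 × √(1/n₁ + 1/n₂)]:

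| Comparison | Noncentrality | Power at 0.05 | Stated |
|---|---|---|---|
| 64 vs 64 | 1.2/0.4243 = 2.83 | 80.1% | 80% |
| 128 vs 128 | 1.2/0.3000 = 4.00 | 97.9% | 98% |
| 128 vs 64 | 1.2/0.3674 = 3.27 | 90.1% | 90% |

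All three reproduce at 0.05. At 0.045 the pooled figures would be 97.6% and 89.3%, so the stated 90% fits 0.05 better. This does not establish the level of the pooled test, because protocol 8.1 also says: "Power calculations are based on a 2-sample t-test with no adjustments for multiple comparisons".

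**3. Correlation between the two tests.** Let v be the variance of one arm mean in one part. The Part 1 contrast for 80 mg has variance 2v.
- 80 mg carried, pooled 80 mg contrast (128 vs 128): variance v, covariance v, correlation v/√(2v·v) = 0.707.
- Only 10 mg carried and tested directly (128 vs 128): covariance v/2, correlation 0.5/√2 = 0.354.
- Only 10 mg carried, but 80 mg retested first (64 vs 128 pooled placebo): variance 1.5v, covariance 1.5v, correlation 1.5/√3 = 0.866.

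**4. Error if either test can count, both at 0.05.** Under the global null, with 80 mg first in Part 1, the Part 1 hierarchy errs only when its 80 mg test rejects. So the error is 0.05 + 0.05 − P(both reject), from the bivariate normal with limits ±1.96:

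| Case | P(both reject) | Two-sided error |
|---|---|---|
| 80 mg carried (alone, or both doses with 80 mg first) | 0.0169 | 0.0831 |
| Only 10 mg carried, tested directly | 0.0058 | 0.0942 |
| Only 10 mg carried, 80 mg retested first | 0.0266 | 0.0734 |

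A simulation of 2,000,000 null trials with the hierarchy at each look gave 0.0825 for the first case and 0.0731 for the third. Half of each total lies in the favourable direction: 4.2%, 4.7% and 3.7%, against 2.5%.

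**5. An unconditional split of 0.005 and 0.045** (limits 2.81 and 2.00). Error is 0.005 + 0.045 − P(both reject):
- 0.0500 − 0.0030 = 0.0470
- 0.0500 − 0.0008 = 0.0492
- 0.0500 − 0.0045 = 0.0455

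All are below 0.05 when the choice of dose does not depend on the Part 1 results. Part 1 power at 0.005 is 49.1%.

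**6. A rule that makes Part 1 formal only when no dose recurs.** Suppose 80 mg is not repeated when it is significant in Part 1, and otherwise is carried and pooled at 0.05. A false claim then occurs when |Z₁| > 1.96 or |Z pooled| > 1.96. That is the event of the first case in step 4, so the error is again 8.3% (simulated 0.0830).

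**The case against.** The strongest reply is that the SAP has broken nothing. It limits itself to Part 1, was written before the Part 2 doses were fixed, and promises a Part 2 SAP that could still specify the pooled test. A Part 1 analysis by dose group is what the protocol plans if no dose recurs. On the other branch the protocol fixes when the final analysis takes place and does not expressly rule out an earlier one. Protocol 8.3 makes the SAP the deciding text, and SAP 2.4 already says what Part 1 is for. This is also a Phase 2 dose-ranging study.

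Much of this stands, and it rules out two stronger readings that a reader might infer.
- *That the SAP contradicts the protocol outright, or slips in a forbidden interim analysis, given that protocol 8.4.6 plans none.* The documents do not support this. The SAP covers one branch and is silent on the other, which is a missing link.
- *That the trial is planned with an error of 8% or 9%.* No document gives the level of the pooled test or says that either result may be claimed, and the pooled plan is itself provisional.

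The reply does not close the gap. The rule that the SAP decides settles which text governs Part 1; it does not allocate alpha. A later SAP could add the link, but only after Part 1 has used the full 0.05 and after a committee that includes sponsor personnel has worked with unblinded Part 1 data (protocol 3.6 and 4.5.2.3). SAP 2.4 cannot settle the status of the p-values while SAP 4.1 and 6.2 say otherwise.

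**Conclusion.** The concern holds as a conditional gap in error control that should be fixed. The SAP claims overall control at 0.05 on Part 1 alone, does not link to the protocol's pooled branch, and gives contradictory signals about the status of the Part 1 p-values.

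The error rises from 5% to 8.3%, 9.4% or 7.3% only under these assumptions: 10 or 80 mg recurs; the pooled test also uses 0.05; either result can count; no dose works; the choice of dose does not depend on Part 1 results; and each arm has its planned 64 subjects per part. If no Part 1 dose recurs, the protocol itself plans a separate Part 1 analysis and the conflict does not arise.

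**What to change.** Before the Dose Selection Committee sees unblinded Part 1 data:

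1. In SAP 4.1 and 6.2, give the Part 1 p-values one status that does not depend on which doses are later chosen. There are two ways.
   - They are nominal and for dose selection only, in every case, in line with SAP 2.4. If a dose recurs, the formal test is the protocol's pooled analysis at 0.05.
   - Alpha is split unconditionally, for example 0.005 in Part 1 and 0.045 at the final analysis. This gives 4.7%, 4.9% and 4.6% in the three cases for a fixed choice of dose.

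   A rule that keeps Part 1 formal only when no dose recurs should not be used, because an unblinded committee decides recurrence and the error can stay at 8.3%.
2. State that the pooled p-value is not adjusted for choosing doses on Part 1 data, and whether the overall 0.05 covers each part or the whole study.
3. Enter the choice in SAP Section 9 and carry it into the Part 2 SAP.

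The cost is wording; no extra subjects are needed. With the first option Part 1 has no formal test, also when no dose recurs, and the stated pooled powers of 98% and 90% stand. With the split, Part 1 power falls from 80% to 49%, and pooled power is 97.6% (128 vs 128) and 89.3% (128 vs 64).
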